#### 9.3.3 Covariate Assessment

Not applicable

#### 9.3.4 Validity and Reliability

Study variables stated in this protocol are objective, relevant to the question under study and are accepted as appropriate by regulatory authorities.

Reports of clinically significant outcomes will receive medical review.

Independent expert adjudication will be sought for any reports of congenital anomaly.

Reporting of exposure is expected to be accurate; subjects with a genetic condition (FH) are likely to be aware of treatments taken for that condition, especially around pregnancy and breast-feeding. The burden of reporting dosing dates is not excessive, as Repatha® is administered regularly, once every two weeks or once monthly.

#### 9.4 Data Sources

Data will be provided by study site staff, utilising subject medical notes to abstract information in order to complete electronic CRFs in the study-specific electronic database, which will be provided by the sponsor.

Medical notes will be patient records at the study site and are also expected to include records from maternity/obstetric units.

#### 9.5 Study Size

The study will collect data on all pregnancies and births in females diagnosed with FH and identified via the specialist centres/networks, where the patient consents to participate. Based on a conservative estimated FH prevalence of 1 in 500, and a national diagnosis rate varying between 70% and 1% (Nordestgaard 2013), the number of subjects identified for inclusion in this study is not expected to be large. The EMA guideline EMEA/CHMP/203927/2005 "GUIDELINE ON RISK ASSESSMENT OF MEDICINAL PRODUCTS ON HUMAN REPRODUCTION AND LACTATION: FROM DATA TO LABELLING" assumes an overall incidence of birth defects of 3% in order to derive the number of first trimester pregnancies exposed to a medicinal product that is needed to exclude a certain level of risk. The Guideline further states that if no increased incidence of malformations is observed within at least 300 first trimester-exposed, prospectively collected pregnancies with known pregnancy outcomes (births or fetopathological examinations) then the conclusion might be reached that the medicinal product is not responsible for a 10-fold or more increase of the overall incidence of malformations. In accordance with the Guideline, this study will endeavour to enrol 300 pregnancies exposed to Repatha in the first trimester in order to meet the primary objective of this study. The maximum number of unexposed pregnancies will be limited to a ratio of 2 unexposed to 1 exposed; ie, the maximum will be 600 unexposed pregnancies. In addition, the maximum of unexposed pregnancies originating from a single country will be limited to the minimum of N = 150 or tenfold the expected proportion of births out of the combined total of live births as reported by the relevant Bureaus of Statistics in the participating countries (Appendix H). For example, the observed number of live births in Norway in 2017

represented 1.5% of the births across all participating countries. Therefore, no more than N = 88 (10 x 1.5% = 15% of 600) unexposed pregnancies will originate from Norway. The observed number of United Kingdom births represents 19.6% of all 2017 live births across all countries; tenfold 19.6% of 600 would exceed the target of 600, therefore the number of unexposed pregnancies from the United Kingdom will be capped at N=150. This will ensure we enrol as many unexposed pregnancies as possible whilst avoiding that unexposed pregnancies will originate from a single country only.

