#### 9.2.3 Subject Eligibility

#### 9.2.3.1 Inclusion Criteria

- Females diagnosed with FH
- Confirmed pregnancy during the study observation period
  - Pregnancies identified retrospectively but within the study period will be included
  - Multiple pregnancies, occurring in the same woman within the study period, will all be included (as separate pregnancies)
- Provided informed consent to follow-up in this study, for subject and their infant(s) born during the study observation period

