#### 9.7.2 Planned Method of Analysis

#### 9.7.2.1 General Considerations

Statistical analyses will be descriptive only. No statistical inference or imputations of missing data are planned.

Subject demographics and baseline characteristics will be summarised. Summary statistics for continuous variables will include the number of subjects, mean, median, standard deviation or standard error, minimum, and maximum. For categorical variables, the frequency and percentage will be reported.

Collection of study data may be both retrospective and/or prospective, depending on the time of enrolment of each study subject during the study observation period. Data obtained from retrospective and prospective subject identification will be reported separately.

Multiple pregnancies, occurring in the same woman within the study period, will be reported as separate pregnancies (with an addition of a relevant footnote in the respective tables, indicating that two or more pregnancies occurred in the same woman).

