#### Comments:

This is a signal detection study and is not powered for statistical significance

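### The 300-pregnancy target claims accordance with the guideline but omits two of its recited conditions: prospective collection and a known outcome

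*Supplement*

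**What the plan says.** Section 9.5 (Study Size) takes its number from a guideline on reproductive risk, with a background birth-defect incidence of 3%. As the protocol recites it, if no increased incidence is seen in "at least 300 first trimester-exposed, prospectively collected pregnancies with known pregnancy outcomes (births or fetopathological examinations", the product may be judged "not responsible for a 10-fold or more increase of the overall incidence of malformations".

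The next sentence claims accordance with that guideline and sets the target: "this study will endeavour to enrol 300 pregnancies exposed to Repatha in the first trimester in order to meet the primary objective". The abstract's sample-size paragraph has the same claim and the same 300, without the words about the primary objective. The unexposed group is "limited to a ratio of 2 unexposed to 1 exposed", a maximum of 600.

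Other sections decide what can enter the 300:

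- Section 9.2.3.1: "Pregnancies identified retrospectively but within the study period will be included". No limit is set on their share. Section 9.1 allows capture after delivery.
- Section 9.9.1 says that retrospective recruits are more likely to have adverse outcomes.
- Section 9.7.2.1: "Data obtained from retrospective and prospective subject identification will be reported separately". Sections 9.7.2.7 and 9.9.2 repeat this.
- Section 9.7.2.2 admits a risk that some patient notes cannot be obtained. Section 9.9.3 nevertheless does not expect missing outcomes. No rate is given.
- Appendix G has a post-partum-enrolled block, a row for pregnancies still continuing at data cut-off, and rows for miscarriage and termination. None of them requires a fetopathological examination.

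**The concern.** The guideline criterion describes evaluable pregnancies and sets three conditions: first-trimester exposure, prospective collection and known outcome. The study's target keeps only the first and counts enrolments. A reader of the size justification would take 300 enrolled to deliver the evidence the guideline describes, and the target as written does not ensure that.

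The study answers a regulator's request (Section 7.2), and this criterion is the only justification given for the number. If the count includes pregnancies that the criterion excludes, the justification does not apply to it. The prospective condition also has substance here, because the protocol itself expects retrospective recruits to carry more adverse outcomes.

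**Working it through.** **1. Can the 300 be reproduced?** No. The protocol gives no alpha, power or formula, and Appendix B states "This is a signal detection study and is not powered for statistical significance". The 300 is a threshold taken from the guideline. Two figures in the same section do reproduce: the unexposed maximum, 2 × 300 = 600, and the Norwegian cap, 10 × 56,633 / 3,859,925 × 600 = 88.03, stated as 88.

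**2. The two counts side by side.**

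| Condition | Guideline, as recited in 9.5 | Study target in 9.5 and abstract |
|---|---|---|
| First-trimester exposure | required | required |
| Prospectively collected | required | not mentioned; retrospective cases eligible |
| Known outcome (birth or fetopathological examination) | required | not mentioned; no allowance for loss |
| What is counted | pregnancies meeting all three | pregnancies enrolled |

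The criterion says at least 300. With exactly 300 enrolled, one retrospective, continuing, lost or unexamined pregnancy puts the qualifying number below it.

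**3. Illustrative size.** Let r be the retrospective share and l the share of the remainder without a qualifying outcome. The documents give neither, so both are assumptions.

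Qualifying number = 300 × (1 − r) × (1 − l)

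- r = 10%, l = 15%: 300 × 0.90 × 0.85 = 229.5, about 230
- r = 40%, l = 25%: 300 × 0.60 × 0.75 = 135

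Enrolment needed for 300 qualifying = 300 / ((1 − r)(1 − l))

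- r = 10%, l = 15%: 300 / 0.765 = 392.2, so 393
- r = 40%, l = 25%: 300 / 0.45 = 666.7, so 667

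**4. Does the smaller number lose the 10-fold exclusion?** A 10-fold rise on 3% is 30%. Exact (Clopper-Pearson) two-sided 95% upper limits at about 3% observed are:

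| Anomalies / pregnancies | Upper limit | Multiple of 3% |
|---|---|---|
| 9/300 | 5.6% | 1.9 |
| 7/230 | 6.2% | 2.1 |
| 4/135 | 7.4% | 2.5 |

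All lie far below 30%. One anomaly in 17 pregnancies already puts the upper limit under 30%. Precision against a 10-fold increase is not lost.

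**5. Direction of bias if retrospective cases were pooled.** Suppose, as an assumption, that they ran at 2 to 3 times 3% and made up 30% of the total. The pooled rate would be 0.7 × 3% + 0.3 × 6% = 3.9%, up to 0.7 × 3% + 0.3 × 9% = 4.8%. That pushes towards a false signal, not false reassurance.

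**The case against.** The strongest reply is that 300 is an aim and does not govern the conduct or analysis of the study. Section 9.1 sets no limit on enrolment, and Section 9.9.2 intends to enrol as many eligible subjects as possible. Sections 6 and 9.7.1.2 end the study ten years after it starts. The objective is to describe anomalies (8.1), with no inference planned (7.3), so it does not depend on 300 qualifying pregnancies. Appendix G already separates pre-partum from post-partum enrolment and has a first-trimester column, so much of the qualifying count can be read from it.

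Most of this stands, and it rules out several stronger readings that a reader might infer:

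- *Enrolment would be declared complete at 300.* No section makes 300 exposed pregnancies a stopping point. Only the unexposed group is capped.
- *The qualifying set must fall below 300.* With exposed enrolment open, it could exceed 300.
- *The guideline conclusion would be drawn from retrospective cases.* Separate reporting is planned in three sections and built into Appendix G.
- *The study would be too small to exclude a 10-fold rise.* Step 4 shows otherwise.

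The reply does not answer the wording of Section 9.5. That section ties 300 enrolled to the guideline and to meeting the primary objective. Calling the study a prospective cohort does not help, because the same Section 9.1 allows capture after delivery. The expectation of complete outcomes in 9.9.3 is unquantified and says nothing about the retrospective share. Separate reporting would reveal a shortfall, but it does not make the 300 a count of qualifying pregnancies. Appendix G also has no marker for fetopathological examination of losses.

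**Conclusion.** The point holds as a fault in how the target is defined and justified. The 300 in Section 9.5 and the abstract is described as accordant with a criterion that it does not apply. Reaching 300 enrolled meets that criterion only if all 300 are prospective and have a birth or fetopathological examination.

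A shortfall is possible but not certain, and its size cannot be taken from the documents. The range of about 135-230 qualifying pregnancies per 300 enrolled rests wholly on the assumed shares of 10-40% retrospective and 15-25% of the rest without a qualifying outcome. What is at stake is conformity with the cited criterion, including its requirement for prospective collection.

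**What to change.** Make one of two changes, in both Section 9.5 and the abstract.

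1. **Redefine the count.** Count towards 300 only prospectively enrolled, first-trimester-exposed pregnancies with a known outcome (birth or fetopathological examination). Report that count in each annual report and in the feasibility report (Section 9.7.1.1), with retrospective pregnancies shown outside it. Appendix G would need a marker for losses with a fetopathological examination.
2. **Restate the claim.** Keep 300 as the number enrolled. State the expected qualifying number, the assumed shares behind it and the resulting precision. Delete the words claiming accordance with the guideline.

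The cost is wording and one line in the reports. The stated evidence base becomes less favourable. The second option needs no extra enrolment. Under the first, reaching 300 qualifying pregnancies would take more than 300 enrolled whenever any do not qualify: 393 to 667 under the assumptions used here.

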#### 9.6 Data Management

Data are abstracted by site staff from subject notes into an electronic database provided by the sponsor. The sponsor provides protocol-specific training to all site staff delegated to abstract subject data. An eCRF Completion Guideline is provided.

The Amgen representative(s) and regulatory authority inspectors are responsible for contacting and visiting the Investigator for the purpose of inspecting the facilities and, upon request, inspecting the various records of the clinical study (eg, CRFs and other pertinent data) provided that subject confidentiality is respected.

The Clinical Monitor or designee is responsible for verifying the CRFs at regular intervals throughout the study to verify adherence to the protocol completeness, accuracy, and consistency of the data; and adherence to local regulations on the conduct of research. The Clinical Monitor, or designee is to have access to subject medical records and other study-related records needed to verify the entries on the CRFs in accordance with the local laws and regulations.

The Investigator agrees to cooperate with the Clinical Monitor, or designee to ensure that any problems detected in the course of these monitoring visits, including delays in completing CRFs, are resolved.

In accordance with the sponsor's audit plans, this study may be selected for audit by representatives from Amgen's Global Compliance Auditing function (or designees). Review of study-related records will occur to evaluate the study conduct and compliance with the protocol, and applicable regulatory requirements.

Data capture for this study is planned to be electronic:

- All source documentation supporting entries into the electronic CRFs must be maintained and available upon request.
- Updates to electronic CRFs will be automatically documented through the software's "audit trail".
- To ensure the quality of clinical data across all subjects and sites, a clinical data management review is performed on subject data received at Amgen. During this review, subject data is checked for consistency, omissions, and any apparent discrepancies. To resolve any questions arising from the clinical data management review process, data queries and/or site notifications are created in the EDC system database for site resolution and closed by Amgen reviewer.
- The Investigator signs only the Investigator Verification Form for this electronic data capture study. This signature indicates that the Investigator inspected or reviewed the data on the CRF, the data queries, and site notifications, and agrees with the content.

#### 9.6.1 Obtaining Data Files

Not applicable

#### 9.6.2 Linking Data Files

Not applicable

#### 9.6.3 Review and Verification of Data Quality

Automatic edit checks within the database and further manual review by the sponsor help to ensure quality and completeness of the data. Data queries are sent to site for clarification and resolution of discrepancies.

#### 9.7 Data Analysis

#### 9.7.1 Planned Analyses

#### 9.7.1.1 Interim Analyses

The appropriate regulatory authorities will receive:

- Interim reports of all analyses performed, to be submitted annually. (See Appendix G for **an example** Summary Table **template** to be included in the report)
- A feasibility report three years after study commencement, summarising the number of subjects enrolled, any exposure to Repatha® and describing primary and secondary outcome data.

#### 9.7.1.2 Primary Analysis

The primary analysis will be conducted at the end of the study observation period, which is currently scheduled to occur ten years after study commencement.

#### 9.7.2 Planned Method of Analysis

#### 9.7.2.1 General Considerations

Statistical analyses will be descriptive only. No statistical inference or imputations of missing data are planned.

Subject demographics and baseline characteristics will be summarised. Summary statistics for continuous variables will include the number of subjects, mean, median, standard deviation or standard error, minimum, and maximum. For categorical variables, the frequency and percentage will be reported.

Collection of study data may be both retrospective and/or prospective, depending on the time of enrolment of each study subject during the study observation period. Data obtained from retrospective and prospective subject identification will be reported separately.

Multiple pregnancies, occurring in the same woman within the study period, will be reported as separate pregnancies (with an addition of a relevant footnote in the respective tables, indicating that two or more pregnancies occurred in the same woman).

#### 9.7.2.2 Missing or Incomplete Data and Lost to Follow-up

For all study-related parameters, data are recorded as part of pregnancy follow-up in this cardiovascular high-risk population, and a high degree of completeness of follow-up and data recording can be expected. However, the necessity of obtaining data from multiple sources may incur an increased risk of being unable to obtain specific sets of patient notes. Proactive follow-up will also be encouraged.

There will be no imputation **of** missing data.

#### 9.7.2.3 Descriptive Analysis

## 9.7.2.3.1 Description of Study Enrolment

All eligible patients identified at each study site will be invited by the Investigators to provide informed consent to be enrolled into the study.

## 9.7.2.3.2 Description of Subject Characteristics

Subjects are women diagnosed with FH, treated at centres in Europe, South Africa and Australia, with pregnancy confirmed during the study observation period and who provide informed consent to participate in the study.

Exposed subjects are women who received Repatha® during pregnancy and/or breast-feeding; unexposed subjects are women who have not received Repatha® during pregnancy and/or breast-feeding. In infants, exposure may occur in utero and/or via breast milk, within 15 weeks following the date of Repatha® dosing in the mother.

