#### 7.2 Rationale

In light of the limited data available on use of Repatha® in association with pregnancy and/or lactation, this study is being conducted in response to a request by the EMA to

provide data on outcomes of pregnancy in women (and their infants to the age of 12 months) exposed to Repatha® prior to or during pregnancy and/or breast-feeding.

In women of child-bearing age in Europe, South Africa and Australia those most likely to have been identified as requiring Repatha® for control of hypercholesterolaemia are those diagnosed with FH. Introduction of this particular pharmacological intervention in the majority of non-FH women is anticipated to occur beyond reproductive age.

Considering the low rate of FH diagnosis and the small number of Repatha®-exposed pregnancies anticipated to occur, routine pharmacovigilance surveillance based solely on spontaneous reporting is unlikely to provide the information required by the EMA, in the post-launch period. To address this, a separate study is required, with a targeted, proactive approach to identify cases and seek appropriate follow-up of outcomes of pregnancy in women with FH who have received Repatha® during pregnancy and/or breast-feeding.

This multinational observational study is expected to enrol female FH patients, identified in collaboration with specialist physicians and patient groups:

- Females with FH exposed to Repatha® during pregnancy and/or breast-feeding will form the exposed cohort, and
- Females with FH unexposed to Repatha® during pregnancy and breast-feeding will form the internal comparator group. Although no formal comparison of exposed/unexposed subjects is planned, capturing outcomes of pregnancy in a rare population unexposed to Repatha® will provide contemporary reference **data** against which to consider outcomes in exposed pregnancies.

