#### 8.1 Primary Objective

To describe congenital anomalies in infants of females with FH exposed to Repatha® within 15 weeks prior to or during pregnancy, followed to the age of 12 months.

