Exposure is classified as beginning at 15 weeks prior to conception (5 halflives of Repatha), and a single dose of Repatha at any time during pregnancy or breastfeeding is classified as exposure

Section 6: Endpoint definition and measurement	Yes	No	N/A	Page Number(s)
6.1 Does the protocol describe how the endpoints are defined and measured?	$\boxtimes$			Sctn 9.2.2
6.2 Does the protocol discuss the validity of endpoint measurement? (e.g. precision, accuracy, sensitivity, specificity, positive predictive value, prospective or retrospective ascertainment, use of validation sub-study)	$\boxtimes$			Sctn 9.2.2

Comments:

Endpoints will be reported verbatim, coded in ICD10-BPA according to Eurocat classification and independently adjudicated where congenital anomaly is the outcome

Section 7: Confounders and effect modifiers	Yes	No	N/A	Page Number(s)
7.1 Does the protocol address known confounders? (e.g. collection of data on known confounders, methods of controlling for known confounders)				
7.2 Does the protocol address known effect modifiers? (e.g. collection of data on known effect modifiers, anticipated direction of effect)				

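### Section 9.7.2.3.2 classes women by dosing in pregnancy and/or breast-feeding, against the 15-week pre-conception window in the objectives, so women dosed only before conception or only while breast-feeding are placed in the wrong cohort

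*Supplement*

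**What the plan says.** Two rules stand in the current protocol.

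**Cohort wording.** Section 9.7.2.3.2 says "Exposed subjects are women who received Repatha ® during pregnancy and/or breast-feeding". Its counterpart for the comparator is that "unexposed subjects are women who have not received Repatha ® during pregnancy and/or breast-feeding". Section 7.2 builds its exposed group on the same dosing periods, and for the reference group it says "Females with FH unexposed to Repatha ® during pregnancy and breast-feeding will form the internal comparator group"; the Abstract says the same. None of these sentences has a pre-conception window.

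**Objectives and exposure rules.** The primary objective (8.1) covers infants of women "exposed to Repatha ® within 15 weeks prior to or during pregnancy, followed to the age of 12 months". The second secondary objective (8.2) describes pregnancies with no exposure in that same window. Neither mentions breast-feeding. Only the third secondary objective, on infant health and development, includes it. Section 9.3.1 collects dosing from 15 weeks before pregnancy and explains this as five half-lives. The exposure comments in Appendix B read "Exposure is classified as beginning at 15 weeks prior to conception".

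**Reporting and caps.** Section 9.7.2.7 and Appendix G present maternal results in eight columns. One is for unexposed women, one for women who stopped before conception, and one for exposure only during breast-feeding. Section 9.7.2.7 adds that the columns may overlap. Section 9.5 limits unexposed pregnancies to 600 overall and to a cap per country (Appendix H).

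**The concern.** Group membership depends on which section the programmer follows. Two kinds of women change cohort: those dosed only in the 15 weeks before conception, and those dosed only while breast-feeding.

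Under the protocol's own five-half-life reasoning, the first kind may carry drug into early pregnancy. If they count as unexposed, they sit in the group that is meant to supply reference data for exposed pregnancies, and they drop out of the population that the primary objective names. The second kind, counted as exposed, adds pregnancies with no fetal exposure to any pooled exposed group. Both shifts would bring the two groups' figures closer together, which is the unhelpful direction for what Appendix B calls a signal detection study. The primary population would also be misdescribed even if nobody compared the groups.

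**Working it through.** **1. Classify each dosing pattern under each rule.**

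| Dosing pattern | Cohort wording (Abstract, 7.2, 9.7.2.3.2) | Objectives 8.1 and 8.2, anomaly and pregnancy outcomes |
|---|---|---|
| Any dose during pregnancy | exposed | exposed |
| Only in the 15 weeks before conception | unexposed | exposed |
| Only while breast-feeding | exposed | not exposed |
| None in any of these windows | unexposed | not exposed |

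The second and third rows conflict.

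**2. Check 9.7.2.3.2 against itself.** Its next sentence lets an infant be exposed in utero within 15 weeks of a maternal dose. If the last dose was two weeks before conception, the infant can count as exposed and the mother as unexposed. The negative *and/or* in 9.7.2.3.2 also differs from the *and* in 7.2. Read as *or*, a woman dosed only while breast-feeding meets both definitions, because she was not dosed during pregnancy.

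**3. Reproduce the figures that use the word unexposed.**
- Overall maximum: 2 × 300 = 600, as stated in 9.5.
- Country cap: the smaller of 150 and 10 × (country births / 3,859,925) × 600. Norway: 10 × 56,633 / 3,859,925 × 600 = 88.0, so 88. UK: 10 × 755,043 / 3,859,925 × 600 = 1,173.7, so 150. Both match Appendix H.
- Minimum number of countries: 600 / 150 = 4, as in the Appendix H footnote.

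None of these numbers changes when the definitions are aligned. What changes is which women count towards them.

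**4. Size, as illustration only.** The documents give neither the share of either group nor an effect size. Assume a 3% base rate (9.5), a true risk ratio RR for any dose in the objectives' window, a share f of the comparator dosed only before conception, and a share b of a pooled exposed group dosed only while breast-feeding.

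- Comparator rate = 3% × [(1 − f) + f × RR]
- Exposed rate = 3% × [(1 − b) × RR + b]

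With RR = 2, f = 10% and b = 10%: comparator 3.30%, exposed 5.70%, apparent ratio 5.70 / 3.30 = 1.73. For f from 5% to 30% and b from 0% to 20%, the apparent ratio runs from 6.00 / 3.15 = 1.90 to 5.40 / 3.90 = 1.38. With RR = 3 it runs from 9.00 / 3.30 = 2.73 to 7.80 / 4.80 = 1.63.

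For the shares chosen, these attenuations are upper bounds, because they give every dose in the window the same risk. Fifteen weeks as five half-lives implies a half-life of 15 / 5 = 3 weeks. Under simple first-order decline, a dose 12 weeks before conception leaves (1/2)^4 = 6.25% at conception, and one at 15 weeks leaves (1/2)^5 = 3.1%.

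**The case against.** The strongest reply is that the protocol already separates these women where maternal results are shown. Section 9.7.2.7 and Appendix G give each group its own column, and Appendix G has no pooled exposed column to dilute. The permitted overlap is most naturally read as covering the nested exposed columns; placing one woman under both unexposed and stopped-before-conception would defeat the labels. This largely stands for the maternal outcome tables. It does not settle the matter, because the unexposed column is given no definition of its own, so 9.7.2.3.2 is the only text that supplies one, and the columns do not govern the caps or any pooled summary.

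Other parts of the reply also have force. The Abstract and 7.2 say exposed, not received, and can be read together with the window in 9.3.1; the plain conflict is in 9.7.2.3.2. Section 9.1 names an exposure of interest but does not define unexposed. The third secondary objective needs women dosed while breast-feeding, so a study-wide exposed cohort may properly include them; what is missing is a statement that they are not exposed for anomaly and pregnancy outcomes.

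A reader might go further and infer that the exposed sample of 300 shrinks, or that a real signal will be hidden. The documents do not support either. Section 9.5 counts the 300 by first-trimester exposure, so women dosed only before conception or only while breast-feeding are not, on its face, part of it. The 600 is tied to that 300, so breast-feeding-only women do not inflate it. Sections 7.3 and 9.7.2.4 plan no formal comparison, so no planned risk ratio exists to be attenuated.

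**Conclusion.** The contradiction is in the current text and can be confirmed by reading it. Taken literally, 9.7.2.3.2 misclassifies two identifiable groups relative to the objectives. The practical reach is narrower than the wording suggests: the undefined unexposed column, the count towards the 600 and country caps, and any summary that pools exposed and unexposed women. The 300 and the 600 stand.

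The size of any bias cannot be derived from the documents. The apparent ratios of 1.90 to 1.38 for a true ratio of 2 rest on assumed shares, on equal risk across the whole 15-week window, on no effect of breast-feeding-only dosing, and on a two-group comparison that the plan does not make. They show the direction, towards no difference, and are not a forecast. This should be fixed, but it does not undermine the design.

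**What to change.** Reconcile the Abstract, Section 7.2 and Section 9.7.2.3.2 with the objectives:

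- For congenital anomaly and pregnancy outcomes, exposed means at least one dose from 15 weeks before conception to the end of pregnancy; unexposed means no dose in that window.
- Women dosed only while breast-feeding count as unexposed for those outcomes, and as exposed only in the infant (lactation) analysis.
- State that the unexposed column in 9.7.2.7 and Appendix G uses this definition, and keep the separate breast-feeding-only column.
- Apply the same definition when counting towards the 600 and the country caps in 9.5 and Appendix H.

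The cost is protocol wording, one derivation rule and the usual amendment approval. Dose dates are already collected under 9.3 and 9.3.1, so no new data are needed and enrolled women can be reclassified. The change is best made before any cap fills, because women not enrolled for that reason cannot be recovered by re-tabulation.
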